4.2.3.2 Biomarker Research

Our group has previously described the T cell-inflamed tumor microenvironment as a potential predictive biomarker for response to multiple immunotherapies including therapeutic vaccines, anti-CTLA-4, and anti-PD-1/PD-L1 antibodies^{3-8,20}. Our analysis of the tumor microenvironment in patients with melanoma suggests that approximately 35-50% of cases show evidence of spontaneous priming of anti-tumor T cells leading to migration of CD8+ effector T cells into tumor sites. This phenotype has been designated the T cell-inflamed tumor microenvironment and is characterized by expression of T cell markers, chemokines for T cell recruitment, and transcripts indicative of type I IFN signaling^{4,5,7}.

In addition to response prediction, this gene signature is also potentially useful in identifying those that will not respond. Patients harboring non-inflamed tumors therefore require treatment strategies which may modulate the immune response to facilitate the influx of tumor infiltrating lymphocytes (TIL) and conversion from a non-inflamed to an inflamed tumor.

Beyond the tumor microenvironment, aspects of the host (patient) and commensal environment may also have an essential impact on immunity in response to both radiation and anti-PD1 antibody. Host factors of interest regarding the immune response include circulating immune subsets as well as germline DNA sequence and polymorphisms. Further, a growing literature supports a role for commensal microbiota in the immune response to infection and cancer including development of acute versus chronic immune responses and regulatory mechanisms to prevent collateral tissue damage²¹. We and others have proposed that manipulation of the microbiome has the potential ability to modulate the anti-tumor immune response and promote the development of an inflamed tumor microenviroment^{22,23}.

Considering this background, we propose to collect peripheral blood for serum, peripheral blood mononuclear cells, germline DNA, as well as pre-treatment fecal sample and baseline tumor tissue on all patients. Additionally, it is requested that any patients who undergo tumor biopsy during the study have any available tissue forwarded for analysis in comparison of pretreatment and on-/post-treatment tumor microenvironmental factors.

Pending available tissue, biomarker analysis may include the following assays listed below:

Biomarker name		Tissue/Body Fluid Tested
(Facility performing assay)	Assay	and Timing of Assay
Interferon inducible genes (IDO, PD-L1, FoxP3 etc.)	Gene Array	Pre- and post-treatment tumor tissue
University of Chicago Human Immunological Monitoring Core		
PD-L1, CD3, CD8, FoxP3, Ki67, exome sequencing	IHC, exome sequencing	Pre-treatment tumor tissue (or archived FFPE tissue)
University of Chicago Human Immunological Monitoring Core		
Germline DNA	Genotyping for a genome-wide association study (results pooled with subjects from other studies)	Pre-treatment blood

Biomarker name (Facility performing assay)	Assay	Tissue/Body Fluid Tested and Timing of Assay
University of Chicago Human Immunological Monitoring Core		
Gut microbiome sequencing University of Chicago Human Immunological Monitoring Core	Gut microbiome sequencing (results pooled with subjects from other studies)	Pre-treatment stool
Peripheral blood T cell functional activity University of Chicago Human Immunological Monitoring Core	ELISA for IFN-γ after co-culture with Staphylococcal enterotoxin A	Blood before treatment and after 4 doses of pembrolizumab

5.0 METHODOLOGY

5.1 Entry Criteria

5.1.1 Diagnosis/Condition for Entry into the Trial

1. Unresectable or metastatic melanoma with known BRAF mutation status

5.1.2 Subject Inclusion Criteria

In order to be eligible for participation in this trial, the subject must:

- 1. Be willing and able to provide written informed consent for the trial.
- 2. Be \geq 18 years of age on day of signing informed consent.
- 3. Have experienced disease progression during treatment with an anti-PD1/L1 antibody as the treatment regimen immediately prior to accrual to this study or disease progression within 6 months of adjuvant anti-PD1 antibody.
- 4. Have measurable disease based on irRECIST 1.1.
- 5. Have a performance status of 0 or 1 on the ECOG Performance Scale.
- 6. Demonstrate adequate organ function as defined in Table 1.

Table 1 Adequate Organ Function Laboratory Values

System	Laboratory Value
Hematological	
Absolute neutrophil count (ANC)	≥1,500 /mcL
Platelets	≥100,000 / mcL
Hemoglobin	≥8 g/dL or ≥4.96 mmol/L
Renal	
Serum creatinine OR	≤1.5 X upper limit of normal (ULN) OR

Measured or calculated ^a creatinine clearance (GFR can also be used in place of creatinine or CrCl)	≥60 mL/min for subject with creatinine levels > 1.5 X institutional ULN
Hepatic	
Serum total bilirubin	≤ 1.5 X ULN OR
	Direct bilirubin ≤ ULN for subjects with total bilirubin levels > 1.5 ULN
AST (SGOT) and ALT (SGPT)	≤ 2.5 X ULN OR ≤ 5 X ULN for subjects with liver metastases
Albumin	≥2.5 mg/dL
^a Creatinine clearance should be calculated	per institutional standard.

- 7. Female subject of childbearing potential should have a negative urine or serum pregnancy within 72 hours prior to receiving the first dose of study medication. If the urine test is positive or cannot be confirmed as negative, a serum pregnancy test will be required.
- 8. Female subjects of childbearing potential should be willing to use 2 methods of birth control or be surgically sterile, or abstain from heterosexual activity for the course of the study through 120 days after the last dose of study medication (Reference Section 5.7.2). Subjects of childbearing potential are those who have not been surgically sterilized or have not been free from menses for > 1 year.
- 9. Male subjects should agree to use an adequate method of contraception starting with the first dose of study therapy through 120 days after the last dose of study therapy.

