1.0 TRIAL SUMMARY

[figure not shown]
Abbreviated Title	Pembrolizumab and ipilimumab after anti-PD1/L1 antibody
Trial Phase	II
Clinical Indication	Melanoma
Trial Type	Therapeutic
Type of control	Historical
Route of administration	IV
Trial Blinding	None
Treatment Groups	Progression on anti-PD1/L1 antibody (or combination not containing anti-CTLA4),
Number of trial subjects	70
Estimated enrollment period	2 years
Estimated duration of trial	4 years
Duration of Participation	2 years

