2.2 Trial Diagram

3.0 OBJECTIVE(S) & HYPOTHESIS(ES)

3.1 Primary Objective(s) & Hypothesis(es)

(1) **Objective:** To determine the irRECIST* response rate of pembrolizumab with ipilimumab following initial progression to anti-PD1/L1 antibody (or combination not containing anti-CTLA4) in subjects with advanced melanoma.

*For review of irRECIST see Appendix – Section 13.3

Hypothesis: The combination of pembrolizumab and ipilimumab will induce tumor responses in patients who have been previously treated with anti-PD1/L1 antibody

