- 8. Has known active central nervous system (CNS) metastases and/or carcinomatous meningitis. Subjects with previously treated brain metastases may participate provided they are stable (without evidence of progression by imaging for at least four weeks prior to the first dose of trial treatment and any neurologic symptoms have returned to baseline), have no evidence of new or enlarging brain metastases, and are not using steroids for at least 7 days prior to trial treatment. This exception does not include carcinomatous meningitis which is excluded regardless of clinical stability.
- 9. Has active autoimmune disease that has required systemic treatment in the past 2 years (i.e. with use of disease modifying agents, corticosteroids or immunosuppressive drugs). Replacement therapy (eg., thyroxine, insulin, or physiologic corticosteroid replacement therapy for adrenal or pituitary insufficiency, etc.) is not considered a form of systemic treatment. Patients with previous grade III/IV toxicity from immunotherapy that led to treatment discontinuation are excluded.
- 10. Patients with uveal/ocular melanoma are excluded.
- 11. Has known history of, or any evidence of active, non-infectious pneumonitis.
- 12. Has an active infection requiring systemic therapy.
- 13. Has a history or current evidence of any condition, therapy, or laboratory abnormality that might confound the results of the trial, interfere with the subject's participation for the full duration of the trial, or is not in the best interest of the subject to participate, in the opinion of the treating investigator.
- 14. Has known psychiatric or substance abuse disorders that would interfere with cooperation with the requirements of the trial.

- 15. Is pregnant or breastfeeding, or expecting to conceive or father children within the projected duration of the trial, starting with the pre-screening or screening visit through 120 days after the last dose of trial treatment.
- 16. Has received prior therapy with an anti-CTLA4 agent in the unresectable or metastatic disease setting. Prior treatment with ipilimumab in the adjuvant setting is allowed
- 17. Has a known history of Human Immunodeficiency Virus (HIV) (HIV 1/2 antibodies).
- 18. Has known active Hepatitis B (e.g., HBsAg reactive) or Hepatitis C (e.g., HCV RNA [qualitative] is detected).
- 19. Has received a live vaccine within 30 days of planned start of study therapy.

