5.3 Randomization or Treatment Allocation

There is no randomization within the study however study participants will be allocated to a treatment arm based on prior progressive disease on anti-PD1/L1 antibody alone or PD1/L1 combination not including CTLA4 Ab.

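### The entry criteria do not carry over the objective's bar on an anti-CTLA4 partner in the qualifying regimen when that regimen was adjuvant

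*Combined protocol and SAP*

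**What the plan says.** Three places define the population by the regimen on which the patient progressed:

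- Section 1.0, treatment groups: "Progression on anti-PD1/L1 antibody (or combination not containing anti-CTLA4".
- Section 3.1, primary objective: response rate "following initial progression to anti-PD1/L1 antibody (or combination not containing anti-CTLA4) in subjects with advanced melanoma".
- Section 5.3, allocation: "prior progressive disease on anti-PD1/L1 antibody alone or PD1/L1 combination not including CTLA4 Ab".

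None of these is an entry criterion. Enrolment is decided by sections 5.1.2 and 5.1.3:

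- Inclusion 3 has two limbs, one for the immediately preceding regimen and one for adjuvant treatment. It asks for progression on an anti-PD1/L1 antibody "as the treatment regimen immediately prior to accrual to this study or disease progression within 6 months of adjuvant anti-PD1 antibody". Neither limb mentions partner drugs.
- Exclusion 16 applies to a patient who "Has received prior therapy with an anti-CTLA4 agent in the unresectable or metastatic disease setting". It then adds: "Prior treatment with ipilimumab in the adjuvant setting is allowed".

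Section 10.1 treats any eligible patient who receives a dose of the two drugs in combination as evaluable. It plans no separate analysis by prior regimen.

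**The concern.** The trial asks whether adding ipilimumab produces responses after progression on PD-1/PD-L1 blockade without CTLA-4 blockade. A patient who relapsed soon after receiving both classes together is a different case, and the objective's parenthesis leaves that case out. If the entry criteria let the patient in, the primary response rate is estimated in a population other than the one stated. The analysis plan gives no means of telling these patients apart.

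If they respond less often than the target population, the observed rate is pulled down and the two-stage rule (stop at 1 or fewer of 12; 6 or more of 35 needed to reject) becomes harder to meet. If they respond equally well, power is unaffected, but the result still does not describe the stated population.

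**Working it through.** **Step 1: does any criterion close the gap?** Take a patient who relapsed 3 months after the end of adjuvant anti-PD1 plus ipilimumab and has had no other systemic therapy.

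| Criterion | Effect on this patient |
|---|---|
| Inclusion 3, adjuvant limb | Met: relapse within 6 months of adjuvant anti-PD1; a partner drug is not addressed |
| Exclusion 16 | Not triggered: no anti-CTLA4 in unresectable or metastatic disease, and adjuvant ipilimumab is permitted |
| Exclusion 1 | A 4-week washout of trial therapy; its non-CTLA-4 wording only defines who is exempt from the washout |
| Exclusion 5 | A 4-week washout of monoclonal antibodies, passed at 3 months |
| Exclusion 9 | Applies only if earlier immunotherapy was stopped for grade III/IV toxicity |
| Exclusion 13 | Could apply (earlier therapy that might confound results), but only in the treating investigator's opinion |

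The first limb has the same gap. It is not confined to metastatic treatment, so progression during adjuvant anti-PD1 plus ipilimumab also fits once the washout has passed. Metastatic anti-CTLA4 combinations are barred by exclusion 16, so the problem is confined to the adjuvant setting. Adjuvant ipilimumab followed later by progression on anti-PD1 alone is consistent with both the objective and the criteria.

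**Step 2: reproduce the plan's design (section 10.1).** Inputs: 12 patients, stop at 1 or fewer responses; 23 more; reject at 6 or more of 35; response rates 10% and 30%.

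- P(stop early) = P(X1 ≤ 1), with X1 ~ Bin(12, p).
- P(reject) = Σ over x from 2 to 12 of P(X1 = x) × P(X2 ≥ 6 − x), with X2 ~ Bin(23, p).

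At p = 0.10, early stopping is 0.659 (stated 0.65) and P(reject) is 0.098 (stated alpha 0.10). At p = 0.30, power is 0.901 (stated 90%) and the chance of stopping at stage 1 is 0.085. The design figures stand.

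**Step 3: illustration.** The documents give neither the number of such patients, k, nor their response rate, q. Both are assumed. With the other patients at 30%, the mean rate is p = [0.30 × (35 − k) + q × k] / 35. For k = 4 and q = 0 this is 0.30 × 31 / 35 = 0.266. The same mean rate is used in both stages.

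| k of 35 | q | Mean rate | P(stop at stage 1) | Power |
|---|---|---|---|---|
| 0 | – | 0.300 | 0.085 | 0.901 |
| 1 | 0% / 10% | 0.291 / 0.294 | 0.095 / 0.092 | 0.888 / 0.893 |
| 2 | 0% / 10% | 0.283 / 0.289 | 0.106 / 0.099 | 0.873 / 0.883 |
| 4 | 0% / 10% | 0.266 / 0.277 | 0.131 / 0.114 | 0.836 / 0.861 |
| 6 | 0% / 10% | 0.249 / 0.266 | 0.161 / 0.131 | 0.791 / 0.836 |

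One patient costs about one percentage point of power. Six cost about 7 to 11 points.

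**The case against.** The best defence is that the protocol should be read as a whole. Where it means combinations it says so, and the adjuvant limb names only an anti-PD1 antibody. Read with the objective, that limb admits combinations without anti-CTLA4 and keeps out those with it. Exclusion 13 reaches earlier therapy that might confound the result. Section 7.2 adds a check of source documents before treatment and lets the principal investigator clarify criteria. The documents mention adjuvant anti-PD1 and adjuvant ipilimumab only separately and never describe the two given together. If such patients do respond less, the error is conservative, since a false positive becomes less likely.

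Much of this stands. A careful investigator may well reach the intended reading, so it would be too strong to infer that the patient in step 1 satisfies every criterion regardless: exclusion 13 could be used. Nor do the documents show that relapse after an adjuvant course establishes failure of the combination in measurable disease, so a reader should not conclude that such patients are wholly uninformative.

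The defence does not remove the gap. Exclusion 13 depends on opinion and can differ between sites. Section 7.2 checks documents against the written criteria, which lack the restriction. Reading inclusion 3 as single agent only would also shut out the combinations without anti-CTLA4 that the objective admits. Section 7.1 points to Section 3 for eligibility, which is now the objectives section; this looks like an outdated cross-reference and is not a safe way to import the restriction.

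**Conclusion.** The point holds as a mismatch between the stated population and the eligibility criteria, confined to the adjuvant setting. Followed as written, the criteria can admit a patient outside the objective, who then counts in the primary endpoint. This conclusion rests on the text alone.

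The size is uncertain. The power losses in step 3 depend on assumed numbers and response rates, and the true number may be zero or one. A reader might infer that the trial is materially biased against the combination or that its operating characteristics are misstated; the documents support neither. Nor do they support barring any particular order of separate adjuvant regimens, because the objective restricts only the regimen on which the patient progressed.

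**What to change.** Reconcile sections 1.0, 3.1, 5.1.2, 5.1.3 and 5.3.

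- In both limbs of inclusion 3, add the objective's restriction: the qualifying anti-PD1/L1 antibody was given alone, or with partners other than an anti-CTLA4 agent.
- In exclusion 16, state that the allowance for adjuvant ipilimumab does not cover ipilimumab given as part of the qualifying anti-PD1/L1 regimen. Set no requirement on the order of separate adjuvant regimens.
- If the sponsor does intend to admit these patients, leave the criteria as they are and amend sections 1.0, 3.1 and 5.3 to say so.

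The cost is amendment wording and one line on the eligibility checklist. Under the first route, a few otherwise eligible patients may be turned away. The sample size and decision rule need no change.

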5.1.3 Subject Exclusion Criteria

The subject must be excluded from participating in the trial if the subject:

- 1. Has received study therapy (including investigational device) as part of a clinical trial within 4 weeks of the first dose of treatment, with the exclusion of an anti-PD1/L1 antibody given as either a single agent or non-CTLA-4 antibody containing combination.
- 2. Has a diagnosis of immunodeficiency or is receiving systemic steroid therapy or any other form of immunosuppressive therapy within 7 days prior to the first dose of trial treatment.
- 3. Has a known history of active TB (Bacillus Tuberculosis)
- 4. Hypersensitivity to pembrolizumab or any of its excipients.
- 5. Has had a prior anti-cancer monoclonal antibody (mAb) within 4 weeks prior to study Day 1 (excluding commercial or investigational anti-PD1 or anti-PD-L1 antibodies as single agents) or who has not recovered (i.e., ≤ Grade 1 or at baseline) from adverse events due to agents administered more than 4 weeks earlier.

Patients who have autoimmune adverse events controlled by replacement therapy (i.e. hypothyroidism) due to previous treatment are eligible provided replacement therapy has been initiated and toxicity has returned to Grade 1.

- 6. Has had prior chemotherapy, targeted small molecule therapy, or radiation therapy within 2 weeks prior to study Day 1 or who has not recovered (i.e., ≤ Grade 1 or at baseline) from adverse events due to a previously administered agent.
 - Note: Subjects with ≤ Grade 2 neuropathy are an exception to this criterion and may qualify for the study.
 - Note: If subject received major surgery, they must have recovered adequately from the toxicity and/or complications from the intervention prior to starting therapy.
- 7. Has a known additional malignancy that is progressing or requires active treatment. Exceptions include basal cell carcinoma of the skin or squamous cell carcinoma of the skin that has undergone potentially curative therapy or in situ cervical cancer.
- 8. Has known active central nervous system (CNS) metastases and/or carcinomatous meningitis. Subjects with previously treated brain metastases may participate provided they are stable (without evidence of progression by imaging for at least four weeks prior to the first dose of trial treatment and any neurologic symptoms have returned to baseline), have no evidence of new or enlarging brain metastases, and are not using steroids for at least 7 days prior to trial treatment. This exception does not include carcinomatous meningitis which is excluded regardless of clinical stability.
- 9. Has active autoimmune disease that has required systemic treatment in the past 2 years (i.e. with use of disease modifying agents, corticosteroids or immunosuppressive drugs). Replacement therapy (eg., thyroxine, insulin, or physiologic corticosteroid replacement therapy for adrenal or pituitary insufficiency, etc.) is not considered a form of systemic treatment. Patients with previous grade III/IV toxicity from immunotherapy that led to treatment discontinuation are excluded.
- 10. Patients with uveal/ocular melanoma are excluded.
- 11. Has known history of, or any evidence of active, non-infectious pneumonitis.
- 12. Has an active infection requiring systemic therapy.
- 13. Has a history or current evidence of any condition, therapy, or laboratory abnormality that might confound the results of the trial, interfere with the subject's participation for the full duration of the trial, or is not in the best interest of the subject to participate, in the opinion of the treating investigator.
- 14. Has known psychiatric or substance abuse disorders that would interfere with cooperation with the requirements of the trial.

- 15. Is pregnant or breastfeeding, or expecting to conceive or father children within the projected duration of the trial, starting with the pre-screening or screening visit through 120 days after the last dose of trial treatment.
- 16. Has received prior therapy with an anti-CTLA4 agent in the unresectable or metastatic disease setting. Prior treatment with ipilimumab in the adjuvant setting is allowed
- 17. Has a known history of Human Immunodeficiency Virus (HIV) (HIV 1/2 antibodies).
- 18. Has known active Hepatitis B (e.g., HBsAg reactive) or Hepatitis C (e.g., HCV RNA [qualitative] is detected).
- 19. Has received a live vaccine within 30 days of planned start of study therapy.

Note: Seasonal influenza vaccines for injection are generally inactivated flu vaccines and are allowed; however intranasal influenza vaccines (e.g., Flu-Mist®) are live attenuated vaccines, and are not allowed.

5.2 Trial Treatments

The treatment to be used in this trial is outlined below in Table 2

Table 2 Trial Treatment

Drug	Dose/	Dose	Route of	Regimen/
	Potency	Frequency	Administration	Treatment Period
Pembrolizumab	200 mg per dose	Q3W	IV infusion	Day 1 of each 3 week cycle
Ipilimumab	1 mg/kg	Q3W	IV infusion	Day 1 of each 3 week cycle x 4 treatments

5.2.1 Dose Selection/Modification

5.2.1.1 Dose Selection

The rationale for selection of doses to be used in this trial is provided in Section 4.0 – Background and Rationale.

The dose amount required to prepare ipilimumab will be based on the subject's weight in kilograms (kg).

5.2.1.2 Dose Modification

Adverse events (both non-serious and serious) associated with pembrolizumab and/or ipilimumab exposure may represent an immunologic etiology. These adverse events may occur shortly after the first dose or several months after the last dose of treatment. Pembrolizumab and ipilimumab must be withheld for drug-related toxicities and severe or life-

threatening AEs as per Table 3 below. See Section 5.6.1 for supportive care guidelines, including use of corticosteroids.

All Grade 3-5 adverse events considered possibly, probably or definitely related to study agent(s) must be discussed with the Principal Investigator. All treating clinicians involved in the protocol are welcomed to discuss complicated cases at any time with the Principal Investigator:

[name], PhD
University of Chicago Comprehensive Cancer Center
[contact]

Table 3 Dose Modification Guidelines for Drug-Related Adverse Events

Toxicity	Hold Treatment For Grade	Timing for Restarting Treatment	Discontinue Subject (Includes both drugs unless stated)			
Diarrhea/Colitis		Toxicity resolves to Grade 0-1.	Toxicity does not resolve within 12 weeks of last dose or inability to reduce corticosteroid to 10 mg or less of prednisone or equivalent per day within 12 weeks. For Grade 3 diarrhea/colitis, permanently discontinue ipilimumab			
	4	Permanently discontinue both pembrolizumab and ipilimumab	Permanently discontinue both pembrolizumab and ipilimumab			
AST, ALT, or	2	Toxicity resolves to Grade 0-1	Toxicity does not resolve within 12 weeks of last dose.			
Increased Bilirubin	3-4	Permanently discontinue (see exception below) ¹	Permanently discontinue both pembrolizumab and ipilimumab			
Type 1 diabetes mellitus (if new onset) or Hyperglycemia	T1DM or 3-4	Hold pembrolizumab for new onset Type 1 diabetes mellitus or Grade 3-4 hyperglycemia associated with evidence of beta cell failure.	Resume pembrolizumab when patients are clinically and metabolically stable. Permanently discontinue ipilimumab.			
Hypophysitis	2-3	Toxicity resolves to Grade 0-1	Toxicity does not resolve within 12 weeks of last dose or inability to reduce corticosteroid to 10 mg or less of prednisone or equivalent per day within 12 weeks.			
	4	Permanently discontinue both pembrolizumab and ipilimumab	Permanently discontinue both pembrolizumab and ipilimumab			
Hyperthyroidism	3	Toxicity resolves to Grade 0-1	Toxicity does not resolve within 12 weeks of last dose or inability to reduce corticosteroid to 10 mg or less of prednisone or equivalent per day within 12 weeks.			
	4	Permanently discontinue both pembrolizumab and ipilimumab	Permanently discontinue both pembrolizumab and ipilimumab			
Hypothyroidism	2-4	Therapy with pembrolizumab can be continued while treatment for the thyroid disorder is instituted	Therapy with pembrolizumab and ipilimumab can be continued while treatment for the thyroid disorder is instituted.			
Infusion Reaction	3-4	Permanently discontinue both pembrolizumab and ipilimumab	Permanently discontinue both pembrolizumab and ipilimumab			
Pneumonitis	2	Toxicity resolves to Grade 0-1	Toxicity does not resolve within 12 weeks of last dose or inability to reduce corticosteroid to 10 mg or less of prednisone or equivalent per day within 12 weeks.			
	3-4	Permanently discontinue both pembrolizumab and ipilimumab	Permanently discontinue both pembrolizumab and ipilimumab			
Renal Failure or 2		Toxicity resolves to Grade 0-1	Toxicity does not resolve within 12 weeks of last dose or inability to reduce corticosteroid to 10 mg or less of prednisone or equivalent per day within 12 weeks.			
Nephritis	3-4	Permanently discontinue both pembrolizumab and ipilimumab	Permanently discontinue both pembrolizumab and ipilimumab			
All Other Drug- Related Toxicity ²	3 or Severe	Toxicity resolves to Grade 0-1	Toxicity does not resolve within 12 weeks of last dose or inability to reduce corticosteroid to 10 mg or less of prednisone or equivalent per day within 12 weeks.			
Aciaica Toxicity	4	Permanently discontinue both pembrolizumab and ipilimumab	Permanently discontinue both pembrolizumab and ipilimumab			

Note: Permanently discontinue for any severe or Grade 3 drug-related AE that recurs or any life-threatening event.

1 For patients with liver metastasis who begin treatment with Grade 2 AST or ALT, if AST or ALT increases by greater than or equal to 50% relative to baseline and lasts for at least 1 week then patients should be discontinued.

² Patients with intolerable or persistent Grade 2 drug-related AE may hold study medication at physician discretion. Permanently discontinue study drug for persistent Grade 2 adverse reactions for which treatment with study drug has been held, that do not recover to Grade 0-1 within 12 weeks of the last dose.

Dosing interruptions are permitted in the case of medical / surgical events or logistical reasons not related to study therapy (e.g., elective surgery, unrelated medical events, patient vacation, and/or holidays). Ipilimumab should be permanently discontinued for subject's who fail to complete the full treatment course of ipilimumab within 16 weeks from administration of first dose.

If a subject's study treatment has been interrupted for more than 2 doses of pembrolizumab and/or ipilimumab, the investigator must contact the Principal Investigator to review the subject's condition in order to resume the treatment. Subjects being treated on combination therapy with pembrolizumab plus ipilimumab who require discontinuation of ipilimumab due to toxicity may continue treatment with pembrolizumab after approval from the Principal Investigator. The reason for discontinuation must be recorded.

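### For patients admitted with Grade 2 AST/ALT, Table 3's liver rows set a restart level they did not start at, and they disagree on whether the Grade 3-4 stop has an exception

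*Combined protocol and SAP*

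**What the plan says.** **Who is admitted.** Table 1 in section 5.1.2 sets the AST/ALT limit at "≤ 2.5 X ULN OR ≤ 5 X ULN for subjects with liver metastases". Footnote 1 to Table 3 in section 5.2.1.2 expects some to start at Grade 2, since it opens "For patients with liver metastasis who begin treatment with Grade 2 AST or ALT".

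**Scope.** The table is headed "Table 3 Dose Modification Guidelines for Drug-Related Adverse Events", so it acts on events attributed to the drugs.

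**Liver row, Grade 2.** Grade 2 is listed in the hold column. The restart condition is "Toxicity resolves to Grade 0-1". The last column discontinues if the toxicity has not resolved within 12 weeks of the last dose. The row has no footnote mark and no alternative for a raised baseline.

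**Liver row, Grade 3-4.** These grades are also in the hold column. The restart column reads "Permanently discontinue (see exception below" and carries the mark for footnote 1. The adjacent column discontinues both drugs permanently and has no mark.

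**Footnote 1.** The patient is discontinued "if AST or ALT increases by greater than or equal to 50% relative to baseline and lasts for at least 1 week". The footnote does not say what follows when that trigger is not met.

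**Section 5.6.1, Hepatic.** For Grade 2 events, liver tests are followed until they are back at baseline. The steroid taper starts when the event has improved to Grade 1 or less.

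**The concern.** The protocol knowingly enrols patients at Grade 2 and then measures their recovery against a grade they did not have on day 1. Taken at its word, the Grade 2 row permanently ends treatment in a patient whose drug-related rise has fully reversed. For a rise into Grade 3, two adjacent cells of one row differ on whether there is an exception, and the footnote described as the exception contains only a rule for stopping.

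These rows are likely to be used. Section 4.2.2 reports that ALT elevation was the only dose-limiting event seen in more than one patient in the cited phase I study of this combination. The trial runs at several institutions, so like cases could be handled differently.

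At stake are safety handling and exposure in patients with liver metastases. Ipilimumab exposure is the tighter constraint. Four doses at 3-week spacing span 3 x 3 = 9 weeks, and section 5.2.1.2 requires the course to be complete within 16 weeks of the first dose. That leaves about 16 - 9 = 7 weeks of total delay, so waiting for Grade 0-1 can cost ipilimumab doses before the 12-week limit is reached.

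**Working it through.** The plan gives no figure to reproduce. The check is to apply the cells together to a patient who begins at Grade 2.

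**Step 1: restart level (text alone).** Baseline is Grade 2. A drug-related rise occurs and treatment is held. The rise reverses and the value returns to baseline, which is still Grade 2. The restart condition is Grade 0-1, so it is not met. If the value stays at baseline, the 12-week rule discontinues the patient. No cut-off in ULN is needed. Within section 5.6.1, hepatic monitoring uses baseline as its end point and the taper uses Grade 1 or less, so the supportive-care text does not settle which level counts as recovered. Elsewhere, exclusion criteria 5 and 6 do allow for a raised baseline ("i.e., ≤ Grade 1 or at baseline"), though for recovery from earlier treatment.

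**Step 2: Grade 3-4 row (text alone).** Suppose a rise into Grade 3 does not meet footnote 1, because it is under 50% or shorter than 1 week. There are two readings.
- If the footnote is a true exception, the permanent stop is lifted for this patient. That contradicts the unmarked adjacent cell, and no restart condition is given.
- If the adjacent cell governs, the patient stops and the reference to an exception has no effect.

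**Step 3: illustration.** The documents name CTCAE v4.0 but do not print its AST/ALT limits. Assume that Grade 2 ends and Grade 3 begins at 5 x ULN, and that Grade 2 starts at either 2.5 or 3 x ULN. A 50% rise from a Grade 2 baseline then ends between 1.5 x 2.5 = 3.75 (or 1.5 x 3.0 = 4.5) and 1.5 x 5.0 = 7.5 x ULN. It reaches 5 x ULN from a baseline of 5.0 / 1.5 = 3.33 x ULN, whichever lower limit is used. Below that baseline, any rise into Grade 3 exceeds 50% and only the 1-week condition is in play. Above it, values between 5.0 x ULN and 1.5 x baseline are in Grade 3 without meeting the 50% condition.

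| Baseline to on-treatment (x ULN) | Rise | Duration | Liver row | Footnote 1 trigger | Result |
|---|---|---|---|---|---|
| 3.2 to 4.0 | 4.0/3.2 = 1.25, 25% | any | Grade 2: hold | not met | return to 3.2 does not meet the restart level |
| 3.2 to 4.8 | 4.8/3.2 = 1.50, 50% | 1 week or more | Grade 2: hold | met, stop | can be read in sequence |
| 4.0 to 5.5 | 5.5/4.0 = 1.375, 38% | any | Grade 3-4: stop | not met | unsettled |
| 4.9 to 7.3 | 7.3/4.9 = 1.49, 49% | any | Grade 3-4: stop | not met | unsettled |
| 4.0 to 6.2 | 6.2/4.0 = 1.55, 55% | under 1 week | Grade 3-4: stop | not met | unsettled |
| 4.0 to 6.2 | 55% | 1 week or more | Grade 3-4: stop | met, stop | consistent |

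**The case against.** A reader might infer that the same rise can be read as stop, hold or continue. The documents do not support the last of these. Both liver rows list their grades in the hold column, and the text above the table requires both drugs to be withheld for drug-related toxicities listed there. What is open is what follows the hold.

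Two further conflicts are tempting but do not stand.
- **Brief spike to Grade 4.** This might seem to escape through the 1-week condition. However, the note under the table stops treatment for any life-threatening event without qualification, and nothing lets footnote 1 override it.
- **A 50% rise that stays within Grade 2.** This might seem to be both hold and stop. It can be read as a hold followed by an added stop criterion for this subgroup.

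On the restart level, the other side can say that a Grade 2 baseline caused by metastases is not itself a drug toxicity, so the toxicity has resolved once the value is back at baseline. That is a fair reading, and it means no hold is triggered on day 1. However, the restart condition is expressed as a grade, and the row offers no baseline alternative.

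Section 5.2.1.2 also requires related Grade 3-5 events to be discussed with the Principal Investigator, and requires contact with the Principal Investigator before treatment resumes after more than 2 interrupted doses. This softens the Grade 3-4 problem. The Grade 3-5 requirement does not reach the Grade 2 restart level, and discussion of single cases does not reconcile the written cells.

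**Conclusion.** The concern holds in two respects, both for patients with liver metastases who begin at Grade 2.
1. Read literally, the Grade 2 row permanently stops a patient who has returned fully to baseline.
2. The two columns of the Grade 3-4 row leave it unsettled whether a held patient may restart or must stop after a rise into Grade 3 that is under 50% or shorter than 1 week.

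Both follow from the text; only the illustrative values rest on assumed grade limits. A rise into Grade 3 of at least 50% lasting at least 1 week gives the same answer under both rules.

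The number affected cannot be derived. The documents give neither the share starting at Grade 2 nor the share of those who then have a drug-attributed rise.

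A reader might also infer bias in the primary analysis. The documents do not show it. Section 10.1 counts any eligible patient who receives a dose of the combination, so the response-rate denominator does not change, and the Simon design figures do not depend on these rules. The effect is on safety handling and exposure, and any effect on response is indirect. It is worth correcting because the rules conflict and the correction is cheap.

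**What to change.** Reconcile the liver Grade 2 row, both columns of the Grade 3-4 row, footnote 1 and the hepatic text in section 5.6.1 for patients who begin at Grade 2. State in one place:
- what level counts as recovered for such a patient;
- whether the Grade 3-4 stop has an exception, and what follows the hold when footnote 1 is not met;
- how footnote 1 relates to the Grade 2 row's hold and to the table note on life-threatening events.

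The investigators decide the rule; this review does not propose one.

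The cost is table wording by amendment and a longer footnote. Whether extra tests are needed depends on the rule chosen. The flow chart schedules chemistry once per 3-week cycle, footnote 1 turns on a duration of 1 week, and section 5.6.1 only suggests considering weekly tests.
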